5.3 Lifestyle Considerations

5.3.1 Meals and Dietary Restrictions

5.3.1.1 Diet Restrictions

08X3SB

Participants will fast from all food and drinks, except water, between study intervention administration and the first scheduled meal. Meals and snack(s) will be provided by the investigator at time points indicated in the SoA. Participants will fast from all food and drinks, except water, between meals and snacks. Meals do not have to be identical; however, the caloric content and composition of meals will be the same on each full PK sampling day in each panel. The meal content should be

consistent within a given clinical site.

Approximately 240 mL of water will be provided during study intervention administration. Additional water may be provided in 50-mL increments if required. Water will be restricted 1 hour before and 1 hour after study intervention administration.

On all other days, participants will fast from all food and drinks, except water, for at least 8 hours before study intervention administration. Participants will remain fasted between study drug administration and the first scheduled meal. Meals and snacks will be provided by the investigator at time points indicated in the SoA. Meals and snacks will be unrestricted in caloric content, composition, and timing. Each study intervention administration will need to be taken with approximately 240 mL of water. Additional water may be provided in 50-mL increments if required. Water will be restricted 1 hour before and 1 hour after study intervention administration.

5.3.1.2 Fruit Juice Restrictions

5.3.2 Caffeine, Alcohol, and Tobacco Restrictions

5.3.2.1 Caffeine Restrictions

Participants are advised to refrain from consumption of caffeinated beverages or xanthine-containing products from 12 hours prior to the Screening Visit. A recheck may be needed if participants did not refrain from consuming caffeinated beverages or xanthine-containing products 12 hours prior to the Screening Visit.

On all other days, caffeinated beverages or xanthine-containing products will be limited to no more than 6 units per day (1 unit = 120 mg of caffeine).

5.3.2.2 Alcohol Restrictions

Participants are advised to refrain from consumption of alcohol 24 hours prior to the Screening Visit and 24 hours prior to initial domiciling on Day -3. A recheck may be needed if participations did not refrain from consuming alcohol 24 hours prior to the Screening Visit.

Participants will refrain from consumption of alcohol during their entire sequester in the CRU. At all other times, alcohol consumption is limited to no more than approximately 3 alcoholic beverages or equivalent servings (1 serving is approximately equivalent to: beer [354 mL/12 ounces], wine [118 mL/4 ounces], or distilled spirits [29.5 mL/1 ounce]) per day.

5.3.2.3 Tobacco Restrictions

Smoking (and/or the use of nicotine/nicotine-containing products) is not permitted during the study.

5.3.3 Activity Restrictions

Participants will avoid unaccustomed strenuous physical activity (ie, weightlifting, running, bicycling, etc) from the prestudy (screening) visit until administration of the initial dose of study intervention, throughout the study (including washout intervals between treatment periods), and until the poststudy visit.

Since this study intervention may make participants more likely to get sunburn, they will be required to protect their skin from sunlight exposure.

5.4 Screen Failures

Screen failures are defined as participants who consent to participate in the clinical study but are not subsequently randomized in the study. A minimal set of screen failure information may be included, as outlined in the eCRF entry guidelines. Minimal information may include demography, screen failure details, eligibility criteria, and any AEs or SAEs meeting reporting requirements.

08X3SB

5.5 Participant Replacement Strategy

If a participant discontinues from study intervention or withdraws from the study, a replacement participant may be enrolled if deemed appropriate by the investigator and Sponsor. The replacement participant will generally receive the same intervention or intervention sequence (as appropriate) as the participant being replaced. The replacement participant will be assigned a unique treatment/randomization number.

The replacement participant may begin dosing at the subsequent dose level for that panel, based on investigator and Sponsor review and discussion.

6 STUDY INTERVENTION

Study intervention is defined as any investigational intervention(s), marketed product(s), placebo, or medical device(s) intended to be administered to a study participant according to the study protocol.

Clinical supplies provided by the Sponsor will be packaged to support enrollment and replacement participants as required. When a replacement participant is required, the Sponsor or designee needs to be contacted before dosing the replacement participant. Clinical supplies will be affixed with a clinical label in accordance with regulatory requirements.

6.1 Study Intervention(s) Administered

The study intervention(s) to be used in this study are outlined in Table 3.

Country-specific requirements are noted in Appendix 7.

All supplies indicated in will be provided per the "Sourcing" column depending on local country operational requirements. If local sourcing, every attempt should be made to source these supplies from a single lot/batch number where possible (eg, not applicable in the case where multiple lots or batches may be required due to the length of the study, etc).

Refer to Section 8.1.8 for details regarding administration of the study intervention.

All placebos were created by the Sponsor to match the active product.

6.2 Preparation/Handling/Storage/Accountability

6.2.1 Dose Preparation

There are no specific calculations or evaluations required to be performed to administer the proper dose to each participant. The rationale for selection of doses to be used in this study is in Section 4.3.

6.2.2 Handling, Storage, and Accountability

The investigator or designee must confirm appropriate temperature conditions have been maintained during transit for all study intervention received, and any discrepancies are reported and resolved before use of the study intervention.

Only participants enrolled in the study may receive study intervention, and only authorized site staff may supply or administer study intervention. All study interventions must be stored in a secure, environmentally controlled, and monitored (manual or automated) area in accordance with the labeled storage conditions with access limited to the investigator and authorized site staff.

The investigator, institution, or the head of the medical institution (where applicable) is responsible for study intervention accountability, reconciliation, and record maintenance (ie, receipt, reconciliation, and final disposition records).

For all study sites, the local country Sponsor personnel or designee will provide appropriate documentation that must be completed for drug accountability and return, or local discard and destruction if appropriate. Where local discard and destruction is appropriate, the investigator is responsible for ensuring that a local discard/destruction procedure is documented.

The study site is responsible for recording the lot number, manufacturer, and expiry date for any locally purchased product (if applicable) as per local guidelines unless otherwise instructed by the Sponsor.

The investigator shall take responsibility for and shall take all steps to maintain appropriate records and ensure appropriate supply, storage, handling, distribution, and usage of study interventions in accordance with the protocol and any applicable laws and regulations.

6.3 Measures to Minimize Bias: Randomization and Blinding

6.3.1 Intervention Assignment

Participants will be assigned randomly according to a computer-generated allocation schedule.

The sample allocation tables are provided below in Table 4 and Table 5.

Table 4 Allocation of Participants to Treatment For Panel A

| Number of Participants | Days 1 to 7 | Days 8 to 21 |
|------------------------|--------------------|-----------------------------|
| | Treatment | Treatment |
| n=12 | 6-mg MK-1167 QD + | 3-mg MK-1167 QD + donepezil |
| | donepezil | |
| n=4 | Placebo to MK-1167 | Placebo to MK-1167 |
| | + donepezil | + donepezil |

n=number of participants in a subset of the study; OD=once daily.

The suggested doses may be adjusted downward based on evaluation of safety, tolerability and/or pharmacokinetic data observed in previous treatment periods/panels.

Note: Female participants will be assigned the low allocation range and male participants will be assigned the upper allocation range

Table 5 Allocation of Participants to Treatment For Panel B

| Number of Participants | Days 1 to 31 |
|------------------------|-----------------------------|
| | Treatment |
| n=9 | 6-mg MK-1167 QD + donepezil |
| n=3 | Placebo to MK-1167 |
| | + donepezil |

n=number of participants in a subset of the study; QD=once daily.

The suggested doses may be adjusted downward based on evaluation of safety, tolerability and/or pharmacokinetic data observed in previous treatment periods/panels.

Note: Female participants will be assigned the low allocation range and male participants will be assigned the upper allocation range

6.3.2 Stratification

No stratification based on age, sex, or other characteristics will be used in this study.

6.3.3 Blinding

08X3SB

A double-blinding technique will be used. MK-1167 and placebo will be prepared and/or dispensed in a blinded fashion by an unblinded pharmacist or qualified study-site personnel. The participant, the investigator, and Sponsor personnel or delegate(s) who are involved in the study intervention administration or clinical evaluation of the participants are unaware of the intervention assignments.

Donepezil administration will be conducted as open label; therefore, the Sponsor, investigator, and participant will know the intervention administered.

See Section 8.1.10 for the description of unblinding if a medical emergency occurs during the study.

6.4 Study Intervention Compliance

Interruptions from the protocol-specified treatment plan require consultation between the investigator and the Sponsor and written documentation of the collaborative decision on participant management.

When the individual dose for a participant is prepared from a bulk supply, the preparation of the dose will be confirmed by a second member of the study-site staff.

When participants are dosed at the site, they will receive study intervention directly from the investigator or designee, under medical supervision. The date and time of each dose administered in the clinic will be recorded in the source documents and recorded in the CRF. The dose of study intervention and study participant ID will be confirmed at the time of dosing by a member of the study-site staff other than the person administering the study intervention. Study-site personnel will examine each participant's mouth to ensure that the study intervention was ingested.

6.5 Concomitant Therapy

08X3SB

If a participant does not discontinue all prior medications within 14 days or 5 half-lives of the first dose of study intervention, they may be included in the study if the investigator can rationalize that the specific use of a prior medication is not clinically relevant within the context of the study.

Concurrent use of any prescription or nonprescription medication, or concurrent vaccination, during the ongoing study (ie, after randomization or intervention allocation) must first be discussed between the investigator and Sponsor before administration, unless appropriate medical care necessitates that therapy or vaccination should begin before the investigator and Sponsor can consult. The participant will be allowed to continue in the study if both the Sponsor and the investigator agree.

In addition, the following are specifically restricted from concomitant use during the study:

08X3SB

- All AChEIs other than donepezil (physostigmine, neostigmine, echothiophate, pyridostigmine, rivastigmine, galantamine, tacrine, edrophonium, succinylcholine, etc.).
- All cholinergic agonist medications (pilocarpine, cevimeline, carbachol, bethanecol, etc.).
- All medications with anticholinergic effects (amantadine, atropine, benztropine, cyclobenzaprine, darifenacin, dicyclomine, diphenoxylate with atropine, hydroxyzine, fesoterodine, glycopyrrolate, hydroxyzine, hyoscyamine, ipratropium, oxybutynin, phenothiazine, prochlorperazine, promethazine, quinidine, scopolamine, tolterodine, tropicamide, trospium, trimethobenzamide, trihexyphenidyl, tricyclic antidepressants [amitriptyline, monoamine oxidase inhibitors], as well as antihistamines cyproheptadine, promethazine, desloratadine, loratadine, diphenhydramine, etc.).

- Mood stabilizers, anticonvulsants, and typical or atypical antipsychotic medications (eg, lithium, valproic acid, phenytoin, levetiracetam, carbamazepine) Exception: use of pregabalin and gabapentin for neuropathic pain is acceptable.
- Sedatives/benzodiazepines (eg, chlordiazepoxide, clonazepam, diazepam, flurazepam, meprobamate, triazolam). Use of the following non-benzodiazepine medications for sleep may be acceptable if stable for at least 2 months before the Screening Visit, following review by the investigator and Sponsor: trazodone, mirtazapine, zaleplon, zopiclone, eszopiclone, and zolpidem.
- Narcotic analgesics (eg, codeine, morphine, hydromorphone, oxycodone, propoxyphene and combination products that contain a narcotic).
- Stimulant medications (eg, amphetamine, methylphenidate, atomoxetine, modafinil)

Paracetamol/acetaminophen may be used for minor ailments without prior consultation with the Sponsor.

In addition, the following concomitant medications/vaccinations are permitted:

- Female participants: Hormonal replacement therapy. The participant must be on a stable treatment regimen for at least 6 months prior to screening.
- Cetirizine and montelukast sodium may be permitted for allergies following consultation with the Sponsor.

6.5.1 Rescue Medications and Supportive Care

No rescue or supportive medications are specified for use in this study.

6.6 Dose Modification/Escalation/Other

Refer to Section 4.3.1 for a discussion on the dose planned for this study.

For both Panels A and B, safety and tolerability of at least 8 participants through at least 24 hours post-last dose will be evaluated to determine if study objectives continue to be met.

6.6.1 Stopping Rules

The following stopping rules will be used during the conduct of this study.

These stopping rules apply to study intervention which refers to relationship to MK-1167/placebo administration.

If any of the below stopping rules are met, the study will be stopped, and no further dosing will occur until the Sponsor has reviewed the totality of data available. Continuation of the study would require an amendment.

- An individual participant reports an SAE, unless clearly not related to study intervention by the investigator.
- Two (2) or more participants within a Panel (at the same dose level) report Severe Nonserious AEs unless clearly not related to study intervention by the investigator.

If any of the stopping rules are met, subsequent doses of treatment for remaining participants may be adjusted (maintained at the same level, decreased or halted) based on joint agreement of the Sponsor and investigator after an amendment is implemented.

6.7 Intervention After the End of the Study

There is no study-specified intervention after the end of the study.

6.8 Clinical Supplies Disclosure

The emergency unblinding call center will use the intervention allocation/randomization schedule for the study to unblind participants and to unmask study intervention identity. The emergency unblinding call center should only be used in cases of emergency (see Section 8.1.10). The Sponsor will not provide random code/disclosure envelopes or lists with the clinical supplies.

This study is blinded, but supplies are provided open label; therefore, an unblinded pharmacist or qualified study-site personnel will be used to blind supplies. Study intervention identity (name, strength, or potency) is included in the label text; random code/disclosure envelopes or lists are provided.

6.9 Standard Policies

Not applicable.

08X3SB

7 DISCONTINUATION OF STUDY INTERVENTION AND PARTICIPANT WITHDRAWAL

7.1 Discontinuation of Study Intervention

Discontinuation of study intervention does not represent withdrawal from the study. As certain data on clinical events beyond study intervention discontinuation may be important to the study, they must be collected through the participant's last scheduled follow-up, even if the participant has discontinued study intervention. Therefore, all participants who discontinue study intervention before completion of the protocol-specified treatment period will still continue to participate in the study as specified in Section 1.3 and Section 8.1.9, or a PCL (only applicable if not all procedures should be done per Section 1.3).

Participants may discontinue study intervention at any time for any reason or be discontinued from the study intervention at the discretion of the investigator should any untoward effect occur. In addition, a participant may be discontinued from study intervention by the investigator or the Sponsor if study intervention is inappropriate, the study plan is violated, or for administrative and/or other safety reasons. Specific details regarding procedures to be performed at study intervention discontinuation are provided in Section 8.1.9.

A participant must be discontinued from study intervention, but continue to be monitored in the study, for any of the following reasons:

The participant or participant's legally acceptable representative requests to discontinue study intervention.

The participant's treatment assignment has been unblinded by the investigator, MSD subsidiary, or through the emergency unblinding call center.

The participant interrupts study intervention administration for more than 1 consecutive days or has 1 cumulative missed doses.

The participant has a medical condition or personal circumstance which, in the opinion of the investigator and/or Sponsor, placed the participant at unnecessary risk from continued administration of study intervention.

The participant has a confirmed positive serum pregnancy test.

08X3SB

The participant has a positive drug screen at any time during the course of the study. The drug screen can be confirmed by a recheck at the discretion of the investigator after discussion with the Sponsor.

For a participant who are discontinued from study intervention, all applicable discontinuation activities will be performed according to Section 8.1.9, or if available, a protocol clarification letter.

Discontinuation from study intervention is "permanent." Once a participant is discontinued from study intervention, they shall not be allowed to restart study intervention.

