4.4 Beginning and End-of-Study Definition

The overall study begins when the first participant (or their legally acceptable representative) provides documented informed consent. The overall study ends when the last participant completes the last study-related contact, withdraws consent, or is lost to follow-up (Section 7.3). For purposes of analysis and reporting, the overall study ends when the Sponsor receives the last laboratory test result or at the time of final contact with the last participant, whichever comes last.

If the study includes countries in the European Economic Area (EEA), the local start of the study in the EEA is defined as First Site Ready (FSR) in any Member State.

A study may be paused during review of newly available preclinical/clinical safety, PK, pharmacodynamic, efficacy, or biologic data or other items of interest, prior to a final decision on continuation or termination of the study. It may be necessary to keep the study open for gathering/reviewing of additional supportive data to optimally complete the objective(s) of the study. If necessary, the appropriate amendment(s) to the protocol and/or appropriate communication(s) will be generated. If the decision has been made to end the study following this review period, the study end will be defined as the date of the Sponsor decision, and this end of study date supersedes the definitions outlined above. The Competent Authority(ies) and IRB(s)/IEC(s) will be apprised of the maximum duration of the study beyond the last participant out and the justification for keeping the study open.

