The protocol, protocol amendment(s), informed consent form, investigator's brochure, and other relevant trial documents must be reviewed and approved by an IRB/IEC before being implemented at each site, in compliance with local and/or national regulations and ICH Guidelines. Changes to the protocol that are required urgently to eliminate an immediate hazard and to protect participant safety may be enacted in anticipation of ethics committee approval. MSD will inform regulatory authorities of such new measures to protect participant safety, in compliance with local and/or national regulations.

B. Safety

The guiding principle in decision-making in clinical trials is that participant welfare is of primary importance. Potential participants will be informed of the risks and benefits of, as well as alternatives to, trial participation. At a minimum, trial designs will take into account the local standard of care.

All participation in MSD clinical trials is voluntary. Participants enter the trial only after informed consent is obtained. Trial designs include procedures and systems for the identification, monitoring, and reporting of safety concerns. Participants may withdraw from an MSD trial at any time, without any influence on their access to, or receipt of, medical care that may otherwise be available to them.

During trial planning, the need for an independent Data Monitoring Committee (DMC) is assessed. DMC review of data accumulated during the conduct of the trial is integral to the well-being of trial participants.

C. Confidentiality

MSD is committed to safeguarding participant confidentiality, to the greatest extent possible, as well as all applicable data protection rights. Unless required by law, only the investigator, Sponsor (or individuals acting on behalf of MSD), ethics committee, and/or regulatory authorities will have access to confidential medical records that might identify the participant by name.

D. Genomic Research

Genomic research will only be conducted in accordance with a protocol and informed consent authorized by an ethics committee.

E. Trial Results

At the time of providing informed consent and in accordance with local laws and regulations, participants should be informed about the plans for availability of trial results.

IV. Financial Considerations

A. Payments to Investigators

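### Does the one-missed-dose rule in Section 7.1 conflict with the study-wide dosing stop in Section 6.6.1, and does it need to name the product?

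*Combined protocol and SAP*

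**What the plan says.** Section 7.1 lists reasons for which a participant must be taken off study intervention while follow-up continues. One is that "The participant interrupts study intervention administration for more than 1 consecutive days or has 1 cumulative missed doses". The section then makes the step final: "Once a participant is discontinued from study intervention, they shall not be allowed to restart study intervention".

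Section 6.6.1 sets two study-level stopping rules, one for a serious adverse event and one for two or more severe nonserious events at the same dose level. If either is met, "the study will be stopped, and no further dosing will occur until the Sponsor has reviewed the totality of data available", and the study may continue only by amendment. After that amendment, "subsequent doses of treatment for remaining participants may be adjusted (maintained at the same level, decreased or halted) based on joint agreement" of Sponsor and investigator. Section 10.1.1 says that amendments "must be reviewed and approved by an IRB/IEC before being implemented at each site". Section 4.4 separately notes that "A study may be paused during review of newly available preclinical/clinical safety" and other data, with an amendment or communication if one is needed.

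On product scope, Section 6 gives the general definition: "Study intervention is defined as any investigational intervention(s), marketed product(s), placebo, or medical device(s) intended to be administered to a study participant". Donepezil appears in the intervention table of Section 1.1 and in the allocation tables of Section 6.3.1. Section 6.6.1 adds, for its own purposes, "These stopping rules apply to study intervention which refers to relationship to MK-1167/placebo administration". Section 7.1 carries no such sentence.

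Section 6.4 requires interruptions to be discussed between investigator and Sponsor, and the joint decision to be documented.

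**The concern.** Put side by side, the sections appear to give opposite instructions for the same participant. Suppose a stopping rule is met while someone in Panel B is on Day 10. Dosing is once daily and an amendment needs ethics approval, so at least one dose will not be given. Read literally, Section 7.1 then makes that participant permanently discontinued before any amendment exists, while Section 6.6.1 contemplates that doses may later be maintained.

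The product question compounds this. If the general definition in Section 6 governs Section 7.1, one missed donepezil tablet would end MK-1167 dosing, and the restart ban would reach the participant's background treatment.

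At stake would be on-treatment safety exposure, end-of-dosing PK, the last-day MMSE-2 and DSST scores, and possibly the count of discontinuations due to adverse events, which is part of the primary endpoint in Section 9.3.1.

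**Working it through.** The plan states no figure on this point, so there is none to reproduce. The check is a reading of the text, with dose counts from the stated schedule.

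**Inputs.** Panel A: 7 + 14 = 21 daily doses, 16 participants. Panel B: 31 daily doses, 9 + 3 = 12 participants (Sections 4.1 and 6.3.1). Section 4.2.1.1 already reports Panel A as dosed and well tolerated, so Panel B is the live case.

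**What a conflict requires.** Three readings must hold together:
1. Remaining participants in Section 6.6.1 includes people already in mid-course. The text does not say; participants not yet dosed miss nothing, and for them the sections agree.
2. A dose withheld by a study-wide order is a missed dose. Every other reason in the Section 7.1 list concerns one individual, and the first limb has the participant as its subject. When the protocol itself suspends dosing, it is arguable that no dose is due.
3. The amendment leaves Section 7.1 as it stands. Nothing prevents it from addressing that section.

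Even if all three hold, halting is one of the options Section 6.6.1 lists, so stopping mid-course participants for good complies with both sections.

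**Doses at issue if a stop falls after Day d in Panel B.** Remaining doses = 31 − d.

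| Stop after Day | Doses left | Share of 31 |
|---|---|---|
| 8 | 23 | 74% |
| 15 | 16 | 52% |
| 22 | 9 | 29% |

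At most 12 − 1 = 11 others could be in mid-course; enrolment spacing is not given. The table shows ceilings on the difference between readings. Section 6.6.1 also withholds doses until an amendment is in place, and no text says the rest of the course would then be given.

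**The two limbs of the rule.** Under once-daily dosing, an interruption of more than one day means at least 2 missed doses. The limb triggered by 1 missed dose is always met first, so the other never operates. This is a slip in wording with no effect on who is discontinued.

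**Product scope.** The documents give no miss rate. Assume independent misses at rate q per dose, with q from 0.25% to 2%. In Panel B the chance of at least one missed MK-1167/placebo dose is 1 − (1 − q)^31, or 7.5% to 46.5%. If donepezil also counted and its misses were independent, it is 1 − (1 − q)^62, or 14.4% to 71.4%. Independence overstates the gap: the Schedule of Activities has donepezil taken at about the same time as MK-1167/placebo, so a missed visit would tend to miss both. If misses coincided fully, counting donepezil would add nothing.

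**Analysis.** Section 9.4.1 keeps everyone with at least one dose in the safety population. Section 9.4.2 requires exclusions from the per-protocol set to be listed with reasons. Section 9.3.1 counts discontinuation due to adverse events, so a participant stopped because of someone else's event would ordinarily be recorded under another reason. Section 9.7 states that there is no hypothesis.

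**The case for a change.** The strongest case for a change is that Section 7.1 is mandatory and permanent, and that its missed-dose limb, unlike the limb about interruption, does not depend on who caused the gap. It could be met before any amendment exists, so the amendment would have to undo something the protocol calls final. Doses that are maintained or halted most naturally describe dosing already under way. Section 4.4 allows a pause with an amendment only if necessary, so the amendment argument does not fully cover that route. Sections 6.4 and 8.5 treat interruptions as matters for joint judgement, which sits awkwardly with an automatic stop. Section 6 and the intervention table do support a literal reading that reaches donepezil.

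Part of this stands. Section 7.1 has no express exemption for a Sponsor-ordered stop and names no product. But Section 4.4 speaks of pausing the study before a decision to continue or end it; it does not say that mid-course participants miss doses and then resume, and it provides for a communication where one is needed. Section 6.4 can operate alongside Section 7.1, since consultation and documentation are needed whatever the dosing outcome.

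On donepezil, the visible text treats it as baseline therapy (Section 4.1), an entry condition (Section 5.1) and open label (Section 6.3.3). A ban on a participant's own background drug is an unlikely application of the rule. Table 3, which lists the interventions, is blacked out, so its handling of donepezil cannot be checked. The limiting sentence in Section 6.6.1 concerns attribution of events, so its absence from Section 7.1 is weak evidence of a wider scope there.

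**Conclusion.** The concern identifies a real gap in wording, not a contradiction, and no change to the plan is called for. It matters only if a stopping rule is met, the study is paused, or a donepezil dose alone is missed. In the stop case sites face no conflicting instruction on the day: no dose is given, follow-up continues, and the next step belongs to Sponsor review, joint agreement and an amendment. That amendment is the natural place to reconcile Sections 6.4, 6.6.1 and 7.1 for participants then in mid-course, with the circumstances known. Which rule or threshold applies is the sponsor's clinical decision, and none is suggested here.

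The effect is bounded by 11 participants and the 31 − d doses left to each. How often it would arise cannot be derived from the documents. Studies 001, 003, 004 and 006, as described in Section 2.2.2, report no serious adverse events, though in healthy participants. Section 5.5 permits replacement. The conclusion assumes that discontinuation reasons are recorded individually and that any resumption after a 6.6.1 stop goes through the required amendment. On that footing the descriptive safety and PK results can be interpreted under either reading.
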